NIH IC	NIH Institute or Center
OHRP	Office for Human Research Protections
PI	Principal Investigator
QA	Quality Assurance
QC	Quality Control
SAE	Serious Adverse Event
SAP	Statistical Analysis Plan
SMC	Safety Monitoring Committee
SOA	Schedule of Activities
SOC	System Organ Class
SOP	Standard Operating Procedure
UP	Unanticipated Problem
US	United States

STATEMENT OF COMPLIANCE

The trial will be carried out in accordance with International Conference on Harmonisation Good Clinical Practice (ICH GCP) and the following:

- United States (US) Code of Federal Regulations (CFR) applicable to clinical studies (45 CFR Part 46, 21 CFR Part 50, 21 CFR Part 56, 21 CFR Part 312, and/or 21 CFR Part 812)

The investigators and clinical trial site staff who are responsible for the conduct, management, or oversight of this clinical trial have completed Human Subjects Protection and ICH GCP Training.

The protocol, informed consent form(s), recruitment materials, and all participant materials will be submitted to the Institutional Review Board (IRB) for review and approval. Approval of both the protocol and the consent form must be obtained before any participant is enrolled. Any amendment to the protocol will require review and approval by the IRB before the changes are implemented to the study. In addition, all changes to the consent form will be IRB-approved; a determination will be made regarding whether a new consent needs to be obtained from participants who provided consent, using a previously approved consent form.

1 PROTOCOL SUMMARY

1.1 SYNOPSIS

Title:	Prospective Randomized Evaluation of 14F Thal Tube vs 28 French Chest Tube for Hemothorax and Use of Maximum Barrier Precautions
Phase:	Recruiting
Description of Sites/Facilities Enrolling Participants:	Carolinas Medical Center [name]
Study Description:	Traumatic hemothorax and hemopneumothorax are common diagnoses which are typically treated by placement of a chest tube. A retrospective review has previously shown equivalence between 14 Fr chest tubes and 32 – 40 Fr chest tubes for the non-emergent drainage of hemothorax; however, this study was not randomized. We seek to perform a prospective randomized trial that is adequately powered comparing efficacy of 14 Fr thal tubes to 28 Fr chest tubes for non-emergent drainage of hemothorax and hemopneumothorax. Additionally, we will employ maximal barrier precautions for all chest tube insertions and compare empyema rates to our historical controls for patients with hemothorax, hemopneumothorax, and pneumothorax.
Study Population:	Patients aged 18 and older diagnosed with a traumatic pneumothorax, hemothorax or hemopneumothorax that require non-emergent placement of a thoracostomy tube as part of their care.
Aims:	Aim 1: Determine the safety and efficacy non-inferiority between small bore (14 Fr) and large bore (28 Fr) in the drainage of traumatic hemothorax and hemopneumothorax Aim 2: Determine the incidence of empyema in the setting of traumatic pneumothorax, hemothorax and hemopneumothorax with the addition of maximum barrier precautions [Time Frame: 90 days]
Study Hypothesis	Aim 1: The investigators hypothesize that there is non-inferiority in safety and efficacy between the different chest tube sizes Aim 2: Maximum barrier precautions associated with a decrease in empyema rate.

[figure not shown]
Number of Patients	
Aim 1: With a sample size of n=126 per group, we will have 80% power to detect a non-inferiority margin difference between the group rates of 8% (allowing up to a 15% rate of drainage failure in the small 14 tube size group and approximately 7% in the large 28 tube size group; $\alpha=0.05$).
 
Aim 2: With assumptions of empyema rate is 5% in the retrospective group and 2% in the prospective group, 586 patients in each group are needed to achieve a power of 0.8 with $\alpha=0.05$. To account for potential attrition, we will inflate the number of patients by 10% resulting in a total of 645 patients in the retrospective group and 645 patients in the prospective group.

Inclusion Criteria	
 1. The patient is admitted to the trauma service. 2. The patient has a pneumothorax, hemothorax and/or hemopneumothorax, requiring thoracostomy tube placement. 3. Thoracostomy tube placement is able to be performed or witnessed by an investigator listed on the study. 4. The patient has not had a chest tube in the past year. 5. The patient is ≥ 18 years of age. 6. In the event the patient is decisionally impaired, consent will be obtained from the individual's legally authorized representative (LAR) or from the individual's healthcare power of attorney (HPA). 7. In the instance of reversible impairment, initial consent would be obtained from the LAR/HPA and the patient will be approached for consent once he/she is deemed mentally competent by the care provider.
Exclusion Criteria	
 1. The patient is incarcerated 2. The patient is known to be pregnant 3. The patient is hemodynamically unstable, requiring emergent chest tube placement (in <10 minutes from evaluation). 4. The patient will have more than one chest tube placed at the time of enrollment.

Outcome measures	
Aim I
 
Primary outcome:
 
 • Retained hemothorax requiring an additional intervention, either video-assisted thoracoscopic surgery (VATS) or additional thoracostomy tube placement. 
Secondary outcome:
 
 • Duration of chest tube placement [Time Frame: 90 days] • Length of hospitalization • Subjective pain [Time Frame: 5 minutes pre- and post-insertion], Assessed with 0-10 numeric pain rating scale • Hemodynamic stability post-insertion (determined by vital signs: temperature, heart rate, blood pressure, oxygen saturation) • Initial drainage from chest tube at 5 minutes [Time Frame: 5 minutes] • Tube specific complications: Air leak, tube malposition, & tube migration [Time Frame: 90 days] • Time to radiographic resolution of pneumothorax/hemothorax/hemopneumothorax [Time Frame: 90 days] • Recurrent pneumothorax/hemothorax/hemopneumothorax after tube removal • Readmission for chest tube related complications [Time Frame: 90 days] 
Aim II
 
 • Empyema rates in traumatic pneumothorax, hemothorax, and hemopneumothorax
Description of Study Intervention:	Placement of 14 Fr Thal tube or 28 Fr Chest Tube for Hemopneumothorax.
Study Duration:	2 Years
Randomization	Permuted block randomization with random block sizes to allocate patients in a 1:1 allocation to the 14 or 28 tube sizes. The randomization lists will be generated using SAS Enterprise Guide version 6.1. All study staff collecting and recording data for the trial will be masked to the tube size that was used during the procedure.

Statistical Analysis	
Data Management: All prospectively collected subject data will be recorded in Research Electronic Data Capture application (REDCap) software, collecting insertion specific data including use of a thyroid drape, use of hand scrubbing, gown, mask, sterile gloves, and surgical cap. The chest tube indication will be collected in the REDCap generated survey. The data will be entered into the electronic database within 3 business days of the enrollment or follow-up visit.
 
Statistical procedures for Analysis: All analyses for this randomized trial will follow the intention to treat principle with an additional per protocol analysis given the non-inferiority hypothesis. We will first compare the baseline characteristics of the patients by group to assess for statistically significant or clinically meaningful imbalances. If either exists, these factors will be taken into account in sensitivity analyses for the primary and secondary outcomes. The rates of failure of drainage (primary outcome) will be estimated as proportions and compared between the two groups using a Chi-square test corrected for the non-inferiority hypothesis. We will present the findings using the difference in the proportions (rate in small group – rate in large group) and corresponding 95% upper confidence limit.
 
Length of stay will be compared using Poisson regression with a main effect of group. Post insertion pain and vital signs will be compared using analysis of covariance controlling for pre-procedural pain and vital signs, respectively, with categorical group effect. We will compare rates of re-intervention and readmission using chi-square tests for independence (or Fisher's exact tests) and present our findings using relative risks and 95% confidence intervals.
 
An interim analysis for inferiority will be conducted at 50% and 75% information accrual. This comparison of the primary outcome, failure of drainage, will be compared between the treatment arms with a one-sided test for superiority of the 28 tube compared to the 14 ($\alpha=0.05$).
 
There will be no missing data for the primary outcome as all information will be documented during surgery (no loss to follow up of the patient).

-----------------------------	--

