6 STUDY INTERVENTION

6.1 STUDY INTERVENTION(S) ADMINISTRATION

Screened subjects eligible for study participation will have their inclusion/exclusion criteria verified by an investigator. The subject will be approached for consent by the research staff and enrolled. Subjects with suspected pneumothorax alone will receive either a small bore (14 Fr) or large bore (28 Fr) tube chosen based on physician preference. Subjects with suspected hemothorax or hemopneumothorax will be randomized to receive either a small or large bore chest tube.

Enrolled subjects will have their thoracostomy tube placement procedure observed and verified by an investigator listed on this protocol. The training level of the individual performing the procedure will be recorded. Maximum barrier precautions for this study will be used during the placement procedure for all prospective subjects. Maximum barrier precautions for this study will be defined as the correct use of proper hand hygiene, a cap, surgical gown, sterile gloves, mask, and a thyroid drape. The institutional standard of care thoracostomy tube Practice Guidelines will be followed.

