6.2 INDEX HOSPITALIZATION REVIEW

At the time of enrollment, baseline demographic and injury characteristics will be recorded. Baseline data to be recorded include:

- Demographics (age, sex)
- Vital signs (pre- and post-tube insertion)
- Mechanism of injury (blunt vs penetrating)
- Radiographic findings (pneumothorax, hemothorax or hemopneumothorax)
- Initial laboratory values (hematologic panel, chemistry panel, coagulation panel, toxicology, blood gases)
- Calculated injury severity score

The day of tube insertion will mark study day 0. Subjects will be monitored daily by study staff in the form of chart review for the duration of their hospitalization. A daily data log will be kept for each patient/ The information to be recorded includes:

- Volume of hemo/hemopneumothorax drainage
- Tube misplacement
- Tube migration
- Presence of air leak
- Need for additional thoracostomy tubes

- Need for operative intervention (VATS, thoracotomy)
- Date and time of pneumo/hemo/hemopneumothorax resolution as confirmed by a radiologist
- Date and time of chest tube removal
- Recurrent pnemo/hemo/hemopneumothorax
- Development of infection

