6.4 MEASURES TO MINIMIZE BIAS: RANDOMIZATION AND BLINDING

We will use stratified permuted block randomization with random block sizes to allocate patients in a 1:1 allocation to the 14 or 28 tube sizes. The randomization lists will be generated by a study statistician using SAS Enterprise Guide version 6.1 and stratified by location (Emergency Department and Surgical & Trauma ICU). Randomization lists will be provided to the study coordinator and another study team member not affiliated with clinical care and assessments to place the allocations into number opaque envelopes. These envelopes will be pulled sequentially by the surgeon or study team as a patient is deemed provisionally eligible for the study preserving allocation concealment. The ID of the envelope is recorded in the patient's research record.

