8.3.2 DEFINITION OF SERIOUS ADVERSE EVENTS (SAE)

A serious adverse event (SAE) is an AE occurring during any study phase (i.e., treatment, follow-up), that results in one or more of the following:

- Death
- Life-threatening adverse event
- Inpatient hospitalization or prolongation of existing hospitalization
- Persistent or significant incapacity or disruption of the ability to conduct normal life functions
- Congenital anomaly/birth defect
- An important medical event that may not result in death, be life-threatening, or require hospitalization but may be considered serious when, based upon appropriate medical judgment, they may jeopardize the patient or subject and may require medical or surgical intervention to prevent one of the outcomes listed above.

In this study, we will only be reporting SAEs that are determined to be unexpected and possibly, probably, or definitely related to the size of the initial thoracostomy tube. The principal investigator will assess all potential adverse events for this criteria.

SAEs will be reported in the manner and timeframe that is outlined in the Chesapeake IRB handbook.

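### The synopsis says all data staff are masked to tube size; the plan's own procedures rule that out for some of them, and no section says who is masked or how

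*Combined protocol and SAP*

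**What the plan says.** The only masking statement is in the Randomization row of the synopsis (1.1): "All study staff collecting and recording data for the trial will be masked to the tube size that was used during the procedure". It allows no exception.

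Section 6.4, whose title includes blinding, covers list generation, stratification and sealed envelopes. On who handles the allocation it says "Randomization lists will be provided to the study coordinator and another study team member not affiliated with clinical care and assessments", and then "These envelopes will be pulled sequentially by the surgeon or study team". What goes into the research record is described as "The ID of the envelope is recorded in the" patient's record. The section says nothing about who is masked afterwards.

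Other sections describe the people who see or use the tube:

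- 6.1: "Enrolled subjects will have their thoracostomy tube placement procedure observed and verified by an investigator listed on this protocol".
- 6.2: "Subjects will be monitored daily by study staff in the form of chart review for the duration of their hospitalization".
- 8.3.2: serious events are reported if unexpected and at least possibly "related to the size of the initial thoracostomy tube", and the principal investigator makes that assessment.
- 7.1: the primary care team may replace a tube that drains poorly, and this counts as outcome data.
- 9.4.1: a per-protocol analysis is run alongside intention to treat.
- 4.1: the design is meant to support a comparison of empyema rates by tube size as well as by sterile technique.

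**The concern.** The Aim 1 primary endpoint is retained hemothorax that leads to VATS or another tube. It combines a reading of imaging after 72 hours (4.1) with a decision to intervene. Either part can be influenced by knowing which tube is in place. A reader of the synopsis would credit the trial with protection against detection bias. If the procedures do not deliver that protection, the report claims a design property the trial lacks. This matters in a non-inferiority trial because failures missed in the 14 Fr arm push the result towards the conclusion the trial is set up to reach.

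**Working it through.** **Step 1: test the universal claim against each role.** One data-producing role that must know the tube size is enough to defeat a statement about all staff.

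| Role or task | Section | Must the size be known? |
|---|---|---|
| Judging whether an event relates to tube size | 8.3.2, 8.3.4, 8.3.5 | Yes. The question cannot be answered without it, and the answer is trial data. |
| Recording the size placed, for the per-protocol set | 9.4.1 | Yes, for whoever records it, assuming that set depends on receiving the allocated tube (the plan does not define it). |
| Recording the size placed, for empyema by tube size | 4.1, 6.1 | Yes, for whoever records it. Pneumothorax-only patients get a size by physician preference and have no envelope. By the enrolment targets this is 645 − 252 = 393 prospective patients. |
| Observing and verifying the insertion | 6.1 | The observer sees the tube. The plan does not say whether this person also records outcomes. |
| Pulling the envelope | 6.4 | Whoever opens it knows. It may be the surgeon or the study team. |
| Daily chart review | 6.2 | Probably, since no step hides the size in the chart. This is inference. |
| Day-90 telephone call | 6.3, 7.3 | Not necessarily. |

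The first three rows contradict the claim. The next three make unmasking possible or likely. The last leaves room for a masked role.

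**Step 2: look for a masking procedure.** Section 6.4 describes allocation concealment, which protects assignment before insertion. No section describes masking after insertion, a masked image reading, or separate masked and unmasked database roles.

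**Step 3: illustrate the stakes.** The plan gives no misclassification rate, so the rates below are assumptions.

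Inputs from 9.2: 126 per group, 7% failure with 28 Fr, margin 8 points, α = 0.05. The stated sample size reproduces with α one-sided and equal true rates:

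n = (1.645 + 0.842)² × 2 × 0.07 × 0.93 / 0.08² = 125.8, so 126 per group, power 0.801.

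For recorded rates p₁ (14 Fr) and p₀ (28 Fr):

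P(claim) = Φ[(0.08 − (p₁ − p₀))/SE − 1.645], with SE = √[p₁(1 − p₁)/126 + p₀(1 − p₀)/126].

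*14 Fr failures missed, true rates 15% v 7% (at the margin):*

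| Points missed | Recorded rates | SE | P(false claim), formula | P(false claim), exact binomial with Farrington-Manning test |
|---|---|---|---|---|
| 0 | 15% v 7% | 0.0391 | 0.050 | 0.050 |
| 1 | 14% v 7% | 0.0384 | 0.083 | 0.082 |
| 2 | 13% v 7% | 0.0376 | 0.133 | 0.130 |
| 3 | 12% v 7% | 0.0368 | 0.203 | 0.197 |

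For example, with 2 points missed: (0.08 − 0.06)/0.0376 = 0.532, and Φ(0.532 − 1.645) = 0.133.

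Missing 1 in 10 of the 14 Fr failures only (13.5% v 7%) gives 0.104 by the exact method. Missing 1 in 10 in both arms (13.5% v 6.3%) gives 0.075.

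*14 Fr failures over-called, true rates 7% in both arms (same formula):*

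| Points added | Recorded rates | Power |
|---|---|---|
| 0 | 7% v 7% | 0.801 |
| 1 | 8% v 7% | 0.679 |
| 2 | 9% v 7% | 0.544 |
| 3 | 10% v 7% | 0.413 |

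**The case against.** The best defence is that the sentence is narrower than it looks. It covers staff who collect and record data. It does not cover surgeons, observers, patients or the care team. Unmasked operators can work alongside masked recorders, and parts of the plan fit that reading. The surgeon alone may open the envelope, only the envelope's ID is recorded, and at least one list holder is separate from clinical care and assessments. The insertion items listed for REDCap are barrier precautions and indication, and the daily log in 6.2 does not list tube size. The sentence also sits in the Randomization row, so it may have been meant for Aim 1 only. That would weaken the argument from pneumothorax patients.

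Much of this stands. A reader might infer that every data collector is unmasked, or that the trial is simply open-label. The documents support neither: a masked recorder, caller or image reader is not ruled out, and open-label does not follow from unmasked operators. The defence does not rescue the word all. The principal investigator's event assessment needs the tube size, and so does whoever records the size for the per-protocol set.

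Two further objections are fair. The re-intervention decision belongs to the care team, whom the sentence never covers, so that bias exists whether the sentence is kept, deleted or made true. And VATS or a further tube is a charted event, so a recorder silently omitting one is less plausible than a biased imaging judgement or decision to intervene. The error rates above therefore illustrate what differential ascertainment could do. They do not measure what this sentence does.

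**Conclusion.** The concern holds in limited form. The masking claim, as written, is contradicted by at least one required task and by the need to record the size placed, and no section puts masking into practice. How many recorders are in fact unmasked cannot be settled from the documents.

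The size of any bias is unknown, and its direction could be either way. Under the assumed 1 to 3 points, the false non-inferiority rate is about 8% to 20% instead of 5% if 14 Fr failures are missed. If they are over-called, power falls from 80% to between 68% and 41%. These figures rest on the plan's 126 per group, 7% control rate, 8-point margin and one-sided 0.05, and on misclassification confined to the 14 Fr arm. Correcting the sentence changes neither figure. It changes what the trial can claim about protection from detection bias.

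**What to change.** Replace the sentence in the synopsis, and add the same statement to 6.4:

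- **Unmasked:** operators, observing investigators, the care team, and the principal investigator's event assessment, together with whoever records the size placed.
- **Masked, only if it can be kept so:** for example, the Day-90 caller if kept from the allocation, and a statistician working on coded arm labels until the analysis code is final. Because 6.4 has a study statistician generate the lists, the second role should go to someone else in the biostatistics team.
- **Chart reviewers and imaging:** say whether each is masked. If masked recorders are intended, name the role and say how size is hidden in the chart and database. If not, make no claim for them.

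Report the primary result with the limitation that the re-intervention decision is made knowing the tube size. If a bias figure is given, present it as an illustrative range in both directions.

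The cost is protocol wording and coded labels in the analysis file, with no added patients and no change to care. The downside is that the design is described less favourably.

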1.2 SCHEMA

Figure 1: Study Schema

^a Patients who are GCS = 15 will be approached for consent prior to tube insertion. Patients who are GCS <15 will be approached (or their Legally Authorized Representative (LAR) will be approached) within 24 hours of insertion. If an LAR was used for initial consent, the patient will be consented if and when they become GCS = 15 within the follow up period of the study.

1.3 SCHEDULE OF ACTIVITIES (SOA)

Table 1: Schedule of Activities

Study Requirement	Screening	Treatment Period		Follow Up
		Day 0	Day 1 – Discharge	
Eligibility Criteria	X			
Informed Consent ^a	X			
Demographics and Baseline Injury Characteristics	X			
Randomization		X		
Pain Scores	X	X		
Collect Barrier Precautions Data ^b & Antibiotic status		X		
Thoracostomy Tube Placement		X		
Vital Signs ^c	X (pre-placement)	X (post-placement)		
Hematologic, Chemistry and Coagulation Panel Labs	X			
Arterial Blood Gas Data (if applicable)	X			
Toxicology ^d	X			
Injury Severity Score	X			
Measurement of Chest Tube Drainage		→		
Record Date & Time of PTX/HTX or HPTX Resolution ^e		→		

^a Patients who are GCS = 15 will be approached for consent prior to tube insertion. Patients who are GCS <15 will be approached (or their Legally Authorized Representative (LAR) will be approached) within 24 hours of insertion. If an LAR was used for initial consent, the patient will be consented if and when they become GCS = 15 within the follow up period of the study.

^bBarrier precautions recorded include hand hygiene, cap, gown, gloves, mask and thyroid drape

^cAssessed 5 minutes before and after insertion of thoracostomy tube

^dSerum and urine toxicology will be screened for ethanol, amphetamines, barbiturates, benzodiazepines, cocaine, marijuana and opiates only if it is done as standard of care treatment for that patient.

^eRadiologist-confirmed resolution of pneumothorax (PTX), hemothorax (HTX) and hemopneumothorax (HPTX)

Study Requirement	Screening	Treatment Period		Follow Up Day 90
		Day 0	Day 1 – Discharge	
Collect Data on Thoracostomy Tube Misplacement, Air Leak, & Migration				→
Collect Data on Additional Thoracostomy Tubes				→
Assess for Empyema and Fibrothorax				→
Collect Operative Interventions data ^f				→
Record Critical Care and Hospital Stay Parameters ^g				X
Survival				X
Hospital Readmissions				X
Adverse Events/ Serious Adverse Events				→

^fRefers to video-assisted thoracoscopic surgery (VATS), thoracotomy or thoracostomy tube replacement

^gHospital length of stay (days), ICU stay (days), Mechanical ventilation days

